The HA and rS antigen levels to be studied (and input for the DoE modeling) were selected based on benefit-risk assessment, accounting for past safety, immunogenicity, and manufacturing experience, while simultaneously allowing study of the maximum/widest antigen ranges possible. The design was constrained by the need for simplicity (keeping antigen doses 1 and 2 the same), both to minimize human error during administration of the eventual selected formulation/presentation, and to reduce manufacturing complexity. Four dose levels of HA/strain were chosen for this study: 5, 10, 35, and 60 µg HA/strain. The choice of the lowest HA/strain was informed by the lowest dose likely to induce an adequate HAI antibody response, and the choice of the highest dose was informed by the dose shown to induce a robust HAI antibody and antigen-specific CD4+ T-cell response in the prior Phase 3 study of qNIV with Matrix-M1. The two intermediate dose levels of HA/strain were selected by DoE design software which selects ideal intermediate dose levels to allow optimal DoE modeling. Likewise, 3 dose levels of SARS-CoV-2 rS were chosen for this study: 2.5, 7.5, and 22.5 µg. The choice of the lowest rS dose was informed by the lowest dose likely to induce an adequate anti-S antibody response, and the choice of the highest dose was informed by the highest dose assessed in older adults in the Phase 1/2 study of SARS-CoV-2 rS with Matrix-M1 adjuvant. The one intermediate dose level of rS was selected by DoE design software to again allow optimal DoE modeling. The Matrix-M1 dose will be held constant at 50 µg in each of the ICC vaccine groups and this selection is informed by the extensive safety and immunogenicity experience across multiple Matrix-M1 adjuvanted vaccine programs (SARS-CoV-2 rS, RSV, and Ebola virus vaccines), which collectively indicate that 50 µg dose of Matrix-M1 provides an optimal balance of immunogenicity and tolerability when used in a 2-dose regimen.

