### **9.3.3 Analysis of Secondary Immunogenicity Endpoint Using the DoE Approach**

The study's 12 unique vaccine formulations (excluding reference formulations) arose from a DoE approach with the objective to construct one or more response surface models that can provide information on a combination of antigen (both HA and rS) that when combined with 50  $\mu$ g of Matrix-M1 adjuvant will maximize HAI and anti-S immune responses. The combination(s) identified may or may not be the formulations that are studied. The results are intended to inform selection of potential dose levels for further study.

With the analysis to be performed in the PP population (ie, receiving both doses of study material), there are 2 factors studied. These are the nominal amount (in  $\mu$ g) of SARS-CoV-2 rS protein in each dose, and the nominal amount (in  $\mu$ g) of each of four (4) HA strains for influenza strains in each dose. The levels within each factor are as follows:

Factor	Levels
SARS-CoV-2 rS ( $\mu$ g)	2.5, 7.5, 22.5
HA per strain ( $\mu$ g)	5, 10, 35, 60

These levels will be treated as continuous values. The mean reportable values of anti-spike and HAI antibody responses from each vaccine group will be used to build predictive model(s). The regression model(s) will include all main effects, interactions, and quadratic effects that are found to be statistically significant.

Computer software will be used to fit the model(s) for response(s) of interest. Statistical significance of each model parameter (using p-value) will be assessed in constructing a final response surface. The SAP will contain further theoretical and practical issues related to this methodology.

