In anticipation of a future need to immunize against both SARS-CoV-2 and influenza virus in advance of the winter transmission season, Novavax is undertaking development of an ICC (ie, qNIV and SARS-CoV-2 rS with Matrix-M1 adjuvant). An ICC vaccine would address 2 major vaccine-preventable diseases with a single vaccination approach. The initial target

population for ICC vaccine development is older adults because this population bears a disproportionate burden of morbidity and mortality due to both influenza and COVID-19.

The purpose of this Phase 1/2 study is to evaluate the safety and immunogenicity of multiple formulations of ICC vaccines in older adults. The main objective of the study is to identify one or more optimal dose levels of HA and rS antigens administered as a combination vaccine, which minimize both antigen doses and manage any immunologic interference, using a DoE modeling approach.

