7.4 Analysis of Immunogenicity Endpoint Using the DoE Approach

The study's 12 unique vaccine formulations (excluding reference formulations) arose from a DoE approach with the objective to construct one or more response surface models that can provide information on combination(s) of antigen quantities (both HA and rS) that when combined with 50 µg of Matrix-M1 adjuvant will maximize HAI and anti-S immune responses. The combination(s) identified may or may not be the formulations that are currently being studied. The goal of response surface modelling is to establish the relationship between response and one or more factors, using a set of tools to identify factor settings which optimize response. The results are intended to inform selection of potential dose levels for further study. The modelling exercise will consist of a prospectively established set of analyses and may be followed by further exploration. The SAP defines the prospective set of analyses, whereas further exploratory modelling will be described in the clinical study report.

Day 28 (post single dose) and Day 70 (post 2 doses) immune responses will be the data of primary interest for the regression analysis. Participants in the study are baseline seropositive for SARS-CoV-2 and can be expected to have previously exposure to influenza viruses, so baseline antibody levels for the response parameters are likely to vary and be predictive of response at Days 28/70. Therefore, participants with non-missing Day 28/70 and baseline values in the PP Analysis Set for the responses of interest (Section 7.3.1) will be included in the modeling. In response surface modelling, treatment group is not explicitly designated as an independent variable but are indirectly reflected by factor levels that account for the

amount of each antigen (HA or rS) received. These are treated mathematically as coded continuous quantities ranging from -1 to 1. Participants having a lab-confirmed case of influenza (determined via examination of adverse event reporting) or COVID-19 (determined by anti-NP) between Day 0 and Day 70 may be excluded for the modeling to reduce the extra variability arising from such data points.

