Factor (unit)	Role	Lower value	Upper value
SARS-CoV-2 rS (μg)	Continuous	2.5	22.5
HA per strain (μg)	Continuous	5	60

Table 6 shows the planned list of runs identified by the DOE platform within SAS JMP and number of planned replicates per run. The actual number of replicates providing data will be dependent on the enrollment into the study and exclusion of subjects from the PP Analysis Set. Runs 1 and 3, as well as 8 and 14, are identically specified.

Table 6 Planned List of Runs

Run	Replicates	Value for SARS-CoV-2 Factor	Value for HA Factor
1	40	22.5	60
2	40	2.5	10
3	40	22.5	60
4	40	7.5	10
5	40	22.5	10
6	40	7.5	35
7	40	22.5	5
8	40	2.5	60
9	40	7.5	5
10	40	2.5	5
11	40	22.5	35
12	40	2.5	35
13	40	7.5	60
14	40	2.5	60

Factor levels are treated as continuous coded values ranging from -1 to 1 so that each factor contributes equally to predicting the optimal response. The initial full regression model to be run is expressed as:

$$Y = \beta_0 + \beta_1 X_1 + \beta_2 X_2 + \beta_3 X_1 X_2 + \beta_4 X_1^2 + \beta_5 X_2^2 + \varepsilon$$

where:

Y is the response

X1 = coded antigen level for each HA flu strain

X2 = coded antigen level for SARS-CoV-2 rS

X1*X2 = interaction term for HA antigen level and SARS-CoV-2 rS antigen level

ϵ = error term with expected value of 0

SAS JMP will be used to fit a least-squares model for each response indicated in Table XX. Each run's replicate values may or may not be averaged across the subjects in the PP Analysis Set to determine the independent Y value for the run. An examination of the data will guide the decision and it will be documented in the report. Baseline measurement for each replicate may be included as covariate if no averaging is performed for a run's replicates. The initial full model will be run and significance of each term examined. A p-value <0.05 indicates that a term is significant. Non-significant terms will be removed and the resulting reduced model (for each response) will be fitted for exploration with a Predication Profiler tool. Desirability functions (ranging from 0 for lowest level to 1 for highest level) will be used to identify factor settings that optimize the set of responses. Weighting for each response may be considered. Factor setting(s) that lead to the highest overall desirability will be the level of HA and rS that optimize responses in Table XX.

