As a parallel analysis, SAS PROC RSREG will be used to run a response surface model that uses the dataset without first averaging the results of each run across replicates nor incorporating the baseline measurement into a fold-rise (i.e. use the data as-is). In this model, Y would be set as the antibody response value at the time point of interest, with BL being the corresponding measurement at Day 0. X1 and X2 have the same definition as the when the model is fitted within SAS JMP.

Example SAS code:

```
PROC RSREG DATA=X;  
MODEL Y=BL X1 X2 / LACKFIT COVAR=1;  
RUN;
```

The fit of the model is to be assessed by examining the p-value from the lack-of-fit test and plots of residuals for each factor. Significance of main, quadratic and interaction effects will also be assessed and reported.

The canonical analysis results from PROC RSREG provide information on the shape of the response surface. A maximum point is identified on the response surface by all eigenvalues being negative (a second order derivative test).

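### With three rS levels coded in µg, the SAP 7.4 quadratic can report an interior rS maximum for an anti-S response that never falls, and neither planned fit check can show it (minor)

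*SAP*

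**What the plan says.** Protocol 4.3 sets rS at 2.5, 7.5 and 22.5 µg and adds "The one intermediate dose level of rS was selected by DoE design software to again allow optimal DoE modeling". Protocol 9.3.3 says of the factor levels "These levels will be treated as continuous values". SAP 7.4 takes the nominal µg amounts as the two factors, with limits of 2.5 and 22.5 µg for rS in Table 5, and says "Factor levels are treated as continuous coded values ranging from -1 to 1 so that each factor contributes equally to predicting the optimal response". Table 4 gives a logarithm for each response. No transformation of dose is named and no coding formula is given.

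The JMP model has an intercept, two linear terms, one interaction and two squared terms. Terms with p of 0.05 or more are dropped, and then "Factor setting(s) that lead to the highest overall desirability will be the level of HA and rS that optimize responses". A parallel PROC RSREG fit keeps the full quadratic, uses the antibody value with baseline as covariate, and calls a point a maximum when all eigenvalues are negative. On diagnostics, SAP 7.4 says "The fit of the model is to be assessed by examining the p-value from the lack-of-fit test and plots of residuals for each factor". It also says "The combination(s) identified may or may not be the formulations that are currently being studied" and "The results are intended to inform selection of potential dose levels for further study".

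**The concern.** A quadratic through three points bends wherever the three means make it bend. In µg the rS levels are very unevenly spaced: nothing is tested between 7.5 and 22.5 µg, which is three quarters of the coded range. A response that rises quickly and then slowly is therefore likely to be fitted with a peak inside that gap, even if the true response is still rising at 22.5 µg. The optimum may be an untested combination, so the fitted location can enter the report as a finding about dose response when it reflects level spacing and model form. Clean diagnostics would add unwarranted reassurance.

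**Working it through.** **Inputs.** rS 2.5, 7.5, 22.5 µg and HA 5, 10, 35, 60 µg (Protocol 9.3.3); 14 runs of 40 (SAP Table 6); six-term model and p < 0.05 retention (SAP 7.4). The design counts reproduce: 4 × 3 = 12 unique formulations, plus two duplicates = 14 runs, × 40 = 560. The plan states no figure for the location or precision of the optimum.

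**Coding (plain reading).** X2 = (rS - 12.5)/10 gives -1, -0.5, +1. X1 = (HA - 32.5)/27.5 gives -1, -0.818, 0.091, 1.

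**Fitted peak without noise.** Let f be the share of the 2.5-to-22.5 µg rise reached by 7.5 µg. The quadratic c0 + c1·x + c2·x² through (-1, 0), (-0.5, f), (1, 1) has c1 = 0.5 and c2 = (1 - 4f)/3. For f > 0.25 it is concave, with its peak at x = -c1/(2·c2) = 0.75/(4f - 1). The peak is inside the range when 4f - 1 > 0.75, that is f > 0.4375. At f = 1, x = 0.25, which is 12.5 + 10 × 0.25 = 15.0 µg.

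With log-dose coding the levels sit at -1, 0, +1 (7.5 is the geometric midpoint) and the peak is at 0.25/(f - 0.5) for f > 0.5, interior only for f > 0.75.

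True loss at the false peak, relative to 22.5 µg, is 1 - R^(g - 1), where R is the fold rise and g the true curve scaled from 0 at 2.5 µg to 1 at 22.5 µg. For log-linear, g(20) = ln 8 / ln 9 = 0.946, so at R = 2 the loss is 1 - 2^(-0.0536) = 3.6%.

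| True curve (never falls) | f | Peak, µg coding | Peak, log coding | True loss, 1.5- / 2- / 4-fold rise |
|---|---|---|---|---|
| Linear in µg | 25% | 22.5 (edge) | 22.5 (edge) | none |
| Emax, ED50 10 | 46% | 21.25 | 22.5 (edge) | 1.0 / 1.7 / 3.4% |
| Log-linear | 50% | 20.0 | 22.5 (edge) | 2.2 / 3.6 / 7.2% |
| Emax, ED50 5 | 55% | 18.75 | 22.5 (edge) | 2.4 / 4.0 / 7.9% |
| Emax, ED50 2 | 64% | 17.25 | 22.5 (edge) | 2.5 / 4.2 / 8.2% |
| Plateau from 7.5 µg | 100% | 15.0 | 13.0 | 0 |

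(The losses are for the µg-coded peak.)

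**What the fit checks can see.** The 12 cells carry 1 + 3 (HA) + 2 (rS) + 6 (HA-by-rS) degrees of freedom. The model uses 1 + 2 + 2 + 1 = 6. Lack of fit therefore has 6: one for cubic HA, five for HA-by-rS, none for the rS main effect. A rank check agrees: the model has rank 6, still 6 after adding rS level indicators, and 7 after adding HA indicators. Because the rS indicators lie in the model space, residuals average exactly zero at each rS level whatever the true rS curve.

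**How often.** Simulated trials: one response, flat HA, 14 × 40, normal error on log10, planned p < 0.05 removal. The documents give no SD, rise or curve shape for this population, so these are assumptions: SD 0.3 to 0.5 and a 1.5- to 4-fold rise.

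- Interior rS optimum, µg coding: log-linear about 15 to 90%; Emax ED50 5, 19 to 99%; plateau 75 to 100%; linear in µg 0 to 3%.
- Interior rS optimum, log coding: log-linear and Emax ED50 5, 0 to 5%; plateau 45 to 100%.
- Among log-linear trials with a false interior optimum, the 95% CI for the 22.5-minus-7.5 µg difference lay wholly above zero in about 55 to 100% at 2- to 4-fold rises, but in only about 2 to 52% at 1.5-fold.
- Below 15 µg: about 21 to 55% of the plateau's interior optima, and 15 to 23% (in repeated runs) of the log-linear ones at 1.5-fold and SD 0.5.
- Lack-of-fit rejection: about 4 to 6%, which is its nominal size.

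**Response scale.** If Y in RSREG is not logged, a log-linear curve with fold rise R has f = 1/(1 + √R). R = 2 gives f = 0.414 and a vertex at 23.9 µg; R = 4 gives f = 0.333 and 35.0 µg. Both lie beyond the range.

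**The case against.** The strongest reply is that little turns on this.

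- The JMP deliverable is a joint desirability over the ten responses in Table 4, eight of them HAI, optionally weighted. The simulations optimise a single response, so how far the reported rS setting would move was not estimated.
- The lack-of-fit test and the eigenvalue rule are described with the RSREG fit, whose response scale is not stated. Unlogged, the artefact largely disappears at 2-fold and larger rises. SAP 11 and Table 4 suggest logs, but the point is open.
- For a plateau, the most frequent false peak, nothing is lost: every dose from 7.5 µg up gives the same response.
- SAP 1 wants dose levels "which minimize both antigen doses and manage any immunologic interference, using a DoE modeling approach", so the error runs in a direction the sponsor already favours. Arm-level results are reported under SAP 7.2.2, and SAP 1.1 foresees confirmation in a further study.

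All of this stands and limits the size of the point. It does not remove it. Nothing in SAP 7.4 sets the observed level means beside the optimum or gives the optimum an interval, and the eigenvalue rule does not bind the JMP result.

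Two stronger readings are tempting. A reader might take 15.0 to 22.5 µg as a diagnostic range, so that a peak below 15 µg would be genuine. That range holds only for the noise-free fit. A reader might also infer that the trial will select too low an rS dose. The documents do not support this: the results only inform later selection, the optimum is joint, and the losses are small.

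**Conclusion.** The point holds as a minor one that is cheap to repair. The vertex rule follows from three levels, linear µg coding and a log-scale response; the missing degree of freedom follows from three levels alone. Neither needs an assumed SD. The 15 to 90% frequency does depend on the assumed SD, rise and curve, and on treating one response alone. Curves close to linear in µg, or in square-root µg (f = 37%), are unaffected in expectation.

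The consequence is bounded. Among false-peak trials with log-linear or Emax truths (ED50 2 to 10), the median true loss was 3 to 9%. For scale, the standard error of one 40-person mean at SD 0.4 is 0.4/√40 = 0.063 log10, or about 16%.

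The claim concerns the dose curve of rS itself. It says nothing against the interaction term, through which the plan addresses interference between the antigens. If the rS curve differs by HA level, lack of fit may reject, but for that reason.

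**What to change.** In SAP 7.4:

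1. Write the coding formula (if µg is meant, the two expressions in the working) and state whether Y in PROC RSREG is logged.
2. Add one sensitivity fit of the same six-term model with log-dose coding. Report both optima beside the observed means at each rS level and the 22.5-minus-7.5 µg difference with its 95% CI.
3. Report a confidence interval or region for the rS optimum. Where it reaches 22.5 µg, or the two fits disagree, describe the optimum as not distinguishable from the upper edge.
4. State, with no numeric cut-off, that with three rS levels the lack-of-fit test and the rS residual plot do not check the rS curve, and that an interior fitted peak at any location, on either scale, does not by itself show that the response falls. A plateau and a true peak between 7.5 and 22.5 µg can give the same three level means.

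These are reporting statements, not a dose rule. The cost is a few lines and one extra fit; the µg optimum is still reported. Items 2 and 3 do not resolve the plateau: using the µg-fit region, 46 to 100% of plateau trials would still be described as a firm peak, which is why item 4 is needed. The downside is that true peaks near 15 µg are described less firmly. By the same region, a peak at 15 µg stays firm in 22 to 100% of simulated trials (52 to 90% at a 2-fold rise), and one at 10 µg in 99.7 to 100%.

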At the time of the Day 70 analysis, upon final determination of subject exclusions from analysis and data extraction, members of the Novavax Biostatistics team will be unblinded to perform the analysis. Unblinded data include randomization assignment, dosing received at each dosing visit, and immunological testing results. The broader Novavax team will be group-unblinded upon the release of analysis results.

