To incorporate variation in baseline antibody levels, the individual participant fold-rise in anti-spike and HAI antibody responses at each time point (Table 4) would be used to build predictive model(s). However, examination of the data may reveal that using absolute value is more appropriate, with or without considering the baseline value as a predictor. The starting point is a full model that will include all main effects, interactions, and quadratic effects.

Table 4 List of Responses for Response Surface Modelling

Response	Transformation	Goal
Fold-rise (or absolute value) of HAI titer to A/Brisbane/02/2018 [H1N1] pdm09 (homologous strain) at Day 28 relative to Day 0	Logarithm	Maximize
Fold-rise (or absolute value) of HAI titer to A/Kansas/14/2017 [H3N2] (homologous strain) at Day 28 relative to Day 0	Logarithm	Maximize
Fold-rise (or absolute value) of HAI titer to B/Maryland/15/2016 [Victoria] at Day 28 relative to Day 0	Logarithm	Maximize
Fold-rise (or absolute value) of HAI titer to B/Phuket/3073/2013 [Yamagata] at Day 28 relative to Day 0	Logarithm	Maximize
Fold-rise (or absolute value) of IgG by ELISA to SARS-CoV-2 rS at Day 28 relative to Day 0	Logarithm	Maximize
<hr/>		
Fold-rise (or absolute value) of HAI titer to A/Brisbane/02/2018 [H1N1] pdm09 (homologous strain) at Day 70 relative to Day 0	Logarithm	Maximize
Fold-rise (or absolute value) of HAI titer to A/Kansas/14/2017 [H3N2] (homologous strain) at Day 70 relative to Day 0	Logarithm	Maximize
Fold-rise (or absolute value) of HAI titer to B/Maryland/15/2016 [Victoria] at Day 70 relative to Day 0	Logarithm	Maximize
Fold-rise (or absolute value) of HAI titer to B/Phuket/3073/2013 [Yamagata] at Day 70 relative to Day 0	Logarithm	Maximize
Fold-rise (or absolute value) of IgG by ELISA to SARS-CoV-2 rS at Day 70 relative to Day 0	Logarithm	Maximize

Further exploratory modelling may be performed on cell-mediated immunity (CMI) response measures (e.g. homologous SARS-CoV-2 spike-specific or specific HA T-cell counts), as well as antibody responses tested with different assays (e.g. neutralization titers) or on drift strains. These analyses would be specified in a separate document and described in the clinical study report.

There are 2 factors studied (Table 5)—the nominal amount (in μg) of SARS-CoV-2 rS protein in each dose, and the nominal amount (in μg) of each of four (4) HA strains for influenza strains in each dose.

Table 5 List of Factors in Design of Experiments Approach

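### The JMP dose-selection model leaves response scale, baseline term and averaging open until after unblinding, and its default (individual fold-rise, no baseline term) is never more precise than baseline-adjusted log titre

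*SAP*

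**What the plan says.** SAP 7.4 states that it defines the prospective analyses and that later exploration will be described in the study report. For the JMP model it then leaves these points open:

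- **Response scale and baseline.** The starting response is each participant's fold-rise, but "examination of the data may reveal that using absolute value is more appropriate, with or without considering the baseline value as a predictor". Table 4 carries the same either/or for all ten responses.
- **Averaging.** "Each run's replicate values may or may not be averaged across the subjects in the PP Analysis Set". The only rule is "An examination of the data will guide the decision and it will be documented in the report".
- **Baseline covariate.** "Baseline measurement for each replicate may be included as covariate if no averaging is performed for a run's replicates". The written regression equation has no baseline term, although the same section expects baseline to be predictive of response.

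Terms that do not reach p<0.05 are removed. The reduced models then go to the desirability functions that pick the HA and rS levels.

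SAP 1.4 says that at the Day 70 analysis "members of the Novavax Biostatistics team will be unblinded to perform the analysis", and "Unblinded data include randomization assignment, dosing received at each dosing visit, and immunological testing results".

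SAP 7.4 also specifies a parallel PROC RSREG model at participant level, without fold-rise, with the Day 0 value as covariate. SAP Section 10 says the DoE modelling is done mainly in JMP. Neither section says which result governs.

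Protocol 9.3.3 has the models built from group means. SAP Section 12 records a move to separate models per antibody response but does not settle whether replicates are averaged.

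**The concern.** The study's stated main aim is to identify HA and rS dose levels, and this model does that. Its specification decides which terms survive the p<0.05 screen, and the surviving terms shape the surface that the desirability step optimises. If scale, baseline term and averaging are chosen with assignment and immunology results in hand, and without a criterion, a reader cannot tell how far the selected dose depends on that choice.

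The default is also not the efficient one. Fold-rise without a baseline term imposes a slope of exactly 1 on baseline. Where the true slope differs, residual variance is larger than it need be, and a real interference (interaction) term is more likely to be dropped. The SAP already adjusts for baseline in its GMTR and GMEUR comparisons (7.2.1, 7.2.2, 11.2).

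**Working it through.** **The plan's own figure.** SAP 1.2 gives > 99% power with 40 per group for a two-fold difference (0.301 log10). No SD is stated, so this can be neither reproduced nor refuted. A two-sided two-sample comparison needs an SD of at most 0.314 log10 to reach 99%; at SD 0.4 it has 92% and at 0.5 it has 77%. The figure concerns a pair of formulations, not the regression terms.

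**Inputs.** From SAP Table 6: 14 runs, coded −1 to 1 over HA 5–60 µg and rS 2.5–22.5 µg, and six coefficients. From SAP 7.4: p<0.05 to keep a term, taken as two-sided. Assumed, because the documents give no figure: baseline-to-post correlation r of 0.3 to 0.7; post-vaccination SD 0.5 log10; 36 of 40 participants per run in the PP set; interaction coefficients of 0.05 to 0.15 log10. A coefficient β means that the low-to-high HA effect differs by 4β between low and high rS, so 0.08 is 0.32 log10.

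**Step 1: variance.** With post SD s1 and baseline SD s0:

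- fold-rise: s1² + s0² − 2·r·s0·s1
- baseline-adjusted: s1²·(1 − r²)

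With s0 = s1, adjusted over fold-rise = (1 − r²) / [2(1 − r)] = (1 + r)/2, which is 65%, 75%, 85% at r = 0.3, 0.5, 0.7. If s0/s1 runs from 0.7 to 1.3 over the same r, fold-rise variance is 1.00 to 2.10 times the adjusted variance. It equals 1.00 only where the true slope r·s1/s0 is 1.

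**Step 2: interaction term, participant level for both methods.** The Table 6 matrix gives SE = 0.358 × SD / √36.

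- Fold-rise SD = 0.5·√[2(1 − r)] = 0.592, 0.500, 0.387. SE = 0.0353, 0.0298, 0.0231. Residual df = 14 × 36 − 6 = 498.
- Adjusted SD = 0.5·√(1 − r²) = 0.477, 0.433, 0.357. SE = 0.0285, 0.0259, 0.0213. Residual df = 497.
- Critical t is 1.965 for both. Power is from the noncentral t.

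| Interaction (log10) | Fold-rise, r = 0.3/0.5/0.7 | Adjusted, r = 0.3/0.5/0.7 |
|---|---|---|
| 0.05 | 29 / 39 / 58% | 42 / 49 / 65% |
| 0.08 | 62 / 76 / 93% | 80 / 87 / 96% |
| 0.10 | 81 / 92 / 99% | 94 / 97 / >99% |
| 0.15 | 99 / >99 / >99% | >99% throughout |

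**Step 3: averaging, kept separate.** Averaging leaves 14 − 6 = 8 residual df and a critical t of 2.306. Fold-rise power at 0.08 falls further, to 51 / 65 / 86%. With equal run sizes the dose estimates do not move. The cost is degrees of freedom and the individual baseline covariate.

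**Step 4: how many options are distinct.** At participant level with baseline included, fold-rise and absolute log titre are the same model: y − b = Xβ + γb is y = Xβ + (γ + 1)b. Dose coefficients and p-values are identical, as a numerical check confirmed. The choices that matter are baseline in or out, averaging, and, if baseline is left out, fold-rise or absolute value.

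**The case against.** The strongest reply is that the better model is already in the plan. PROC RSREG is specified with code, a lack-of-fit test and reported term significance, so any divergence from JMP would be visible. Section 10 ranks software, not results. This stands in part: the preferred model needs promoting, not inventing. But term removal and desirability are described only for JMP, no rule resolves a disagreement, and the RSREG text says to use the data as they are without stating the log scale of Table 4.

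Second, the work is exploratory. Protocol 9.1 sets no formal hypotheses, the results inform a later study, the averaging decision must be reported, and residual diagnostics can properly guide scale. This limits the consequence but does not supply a decision rule.

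Third, the power gain rests on an assumed SD, correlation and effect. That is correct. It shrinks as r rises and is negligible at 0.15 log10.

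A reader might also infer three stronger things that the documents do not support:

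- **That the default costs the whole gap from 51/65/86% to 80/87/96%.** The first set is averaged fold-rise. The SAP default is individual fold-rise, and averaging is optional.
- **That the sponsor will pick the best-looking version.** Nothing says so. Taking the smallest p over five permitted versions would raise the null error for one term from 5% to 12–14% in simulation, but that is a worst case.
- **That adjusting for the age stratum is needed.** SAP 11.2 adjusts only for pre-vaccination titre, and no gain from age has been shown.

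**Conclusion.** The point holds as a recommended improvement. The JMP specification is open on scale, baseline and averaging. As written, nothing requires these choices to be made blind, and no rule says which of the two models governs.

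The default is never more precise than baseline-adjusted log titre. The direction does not depend on the assumed figures; the size does. At participant level with SD 0.5 log10, equal SDs and 36 per run, the power loss at 0.08 log10 is about 18, 11 and 3 percentage points at r = 0.3, 0.5 and 0.7. Averaging, if used, is a further loss. What is affected is the precision and credibility of dose selection for a later study, not a formal test.

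**What to change.** Before unblinding, amend SAP 7.4 to name one governing model for both JMP and RSREG:

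- Response: participant-level log10 titre or concentration at the visit, with no averaging.
- Predictors: log10 Day 0 value as covariate, plus the five dose terms.
- This model alone feeds term removal and the desirability step.
- State the log scale in the RSREG paragraph.
- Report fold-rise and averaged fits as sensitivity analyses.

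The age stratum already used in randomisation may be added as an optional covariate.

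The cost is SAP wording and one residual degree of freedom. Day 0 values are already collected, and SAP 7.4 already restricts the modelling to participants who have them. The sponsor gives up choosing the governing specification after seeing the data; diagnostics can still be reported beside it.
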